**Table 1. Highly effective methods of contraception (<1% failure rate)**

Barrier/Intrauterine methods	Hormonal Methods

 
Copper T intrauterine device
 
Levonorgestrel-releasing intrauterine system (e.g., Mirena®)a
 
	
 
Implants: Etonogestrel-releasing implants: e.g. Implanon® or Norplant®
 
Intravaginal: Ethinylestradiol/etonogestrel-releasing intravaginal devices: e.g. NuvaRing®
 
Injection: Medroxyprogesterone injection: e.g. Depo-Provera®
 
Combined Pill: Normal and low dose combined oral contraceptive pill
 
Patch: Norelgestromin/ethinyl estradiol-releasing transdermal system: e.g. Ortho Evra®
 
Minipill: Progesterone based oral contraceptive pill using desogestrel: Cerazette® is currently the only highly effective progesterone based pill
 

a This is also considered a hormonal method

## Blood donation

Patients should not donate blood while participating in this study, or for at least 90 days following the last infusion of durvalumab or tremelimumab or 90 days after receipt of the final dose of durvalumab.

### 7.2. Concomitant treatment(s)

The Principal Investigator must be informed as soon as possible about any medication taken from the time of screening until the end of the clinical phase of the study (final study visit). Any concomitant medication(s), including herbal preparations, taken during the study will be recorded in the CRF.

Restricted, prohibited, and permitted concomitant medications are described in the following tables. Refer to IB's Section 6.6 for guidance on management of IP-related toxicities.

#### 7.2.1. Permitted concomitant medications

*Table 2. Supportive medications*

Supportive medication/class of drug	Usage
Concomitant medications or treatments (e.g., acetaminophen or diphenhydramine) deemed necessary to provide adequate prophylactic or supportive care, except for those medications identified as "prohibited," as listed above	To be administered as prescribed by the Investigator
Best supportive care (including antibiotics, nutritional support, correction of metabolic disorders, optimal symptom control, and pain management [including palliative radiotherapy to non-target lesions, etc])	Should be used, when necessary, for all patients
Inactivated viruses, such as those in the influenza vaccine	Permitted

#### 7.2.2. Excluded concomitant medications

*Table 3. Prohibited concomitant medications*

Prohibited medication/class of drug	Usage
Any investigational anticancer therapy other than those under investigation in this study	Should not be given concomitantly whilst the patient is on study treatment
mAbs against CTLA-4, PD-1, or PD-L1 other than those under investigation in this study	Should not be given concomitantly whilst the patient is on study treatment
Any concurrent chemotherapy,	Should not be given concomitantly whilst the patient is on study treatment.

radiotherapy, immunotherapy, or biologic or hormonal therapy for cancer treatment other than those under investigation in this study	(Concurrent use of hormones for non-cancer-related conditions [e.g., insulin for diabetes and hormone replacement therapy] is acceptable. Local treatment of isolated lesions, excluding target lesions, for palliative intent is acceptable [e.g., by local surgery or radiotherapy])
Immunosuppressive medications including, but not limited to, systemic corticosteroids at doses exceeding 10 mg/day of prednisone or equivalent, methotrexate, azathioprine, and tumor necrosis factor- $\alpha$ blockers	
Should not be given concomitantly, or used for premedication prior to the I-O infusions. The following are allowed exceptions:
 
 
• Use of immunosuppressive medications for the management of IP-related AEs,
 
• Use in patients with contrast allergies.
 
• In addition, use of inhaled, topical, and intranasal corticosteroids is permitted.
 
 
A temporary period of steroids will be allowed if clinically indicated and considered to be essential for the management of non-immunotherapy related events experienced by the patient (e.g., chronic obstructive pulmonary disease, radiation, nausea, etc).

Drugs with laxative properties and herbal or natural remedies for constipation	Should be used with caution through to 90 days after the last dose of tremelimumab during the study
Sunitinib	Should not be given concomitantly or through 90 days after the last dose of tremelimumab (acute renal failure has been reported with combination therapy of tremelimumab and sunitinib)
EGFR TKIs	
Should not be given concomitantly.
 
Should be used with caution in the 90 days post last dose of durvalumab.
 
Increased incidences of pneumonitis (with third generation EGFR TKIs) and increased incidence of transaminase increases (with 1st generation EGFR TKIs) has been reported when durvalumab has been given concomitantly.

Live attenuated vaccines	Should not be given through 30 days after the last dose of IP (including SoC)
Herbal and natural remedies which may have immune-modulating effects	Should not be given concomitantly unless agreed by the sponsor

## 8. STUDY PROCEDURES

### 8.1. Schedule of study procedures

Before study entry, throughout the study, and following study drug discontinuation, various clinical and diagnostic laboratory evaluations are outlined. The purpose of obtaining these detailed measurements is to ensure adequate safety and tolerability assessments. Clinical evaluations and laboratory studies may be repeated more frequently if clinically indicated. The Schedules of Assessments during the screening and treatment period is provided following the Protocol Synopsis

#### For durvalumab + tremelimumab combination+radiotherapy

- Tumor efficacy (RECIST) assessment dates are not affected by dose delays and

remain as originally scheduled, as they are based on the date of enrollment (not the date of therapy).

- All other scheduled assessments must be performed relative to the start of the dosing cycle such that all laboratory procedures, etc required for dosing should be performed within 3 days prior to dosing
- Patients may delay dosing under certain circumstances.
- Dosing may be delayed per Toxicity Management Guidelines, due to either an immune or a non-immune-related AE.
- If dosing must be delayed for reasons other than treatment-related toxicity, dosing will resume as soon as feasible
- Dosing intervals of subsequent cycles may be shortened as clinically feasible in order to gradually align treatment cycles with the schedule of tumor efficacy (RECIST) . Subsequent time between 2 consecutive doses cannot be less than 22 days, based on the half-lives of durvalumab and tremelimumab (see current Investigator Brochures for durvalumab and tremelimumab.

### **8.1.1. Screening phase**

Screening procedures will be performed up to 28 days before Day 1 of Week 1, unless otherwise specified. All patients must first read, understand, and sign the IEC-approved ICF before any study-specific screening procedures are performed. After signing the ICF, completing all screening procedures, and being deemed eligible for entry, patients will be enrolled in the study. Procedures that are performed prior to the signing of the ICF and are considered standard of care may be used as screening assessments if they fall within the 28-day screening window.

The following procedures will be performed during the Screening Visit:

- Informed Consent
- Review of eligibility criteria
- Medical history and demographics
- Complete physical exam
- ECOG Performance Status
- Vitals signs, weight and height
- 12-lead ECG (in triplicate [2-5 minutes apart])
- Confirm collection of tumor biopsy
- Review of prior/concomitant medications
- Imaging by CT scan
- Clinical laboratory tests for:

- Clinical chemistry (see Table 4)
- Hematology (see Table 5)
- Urinalysis (see Table 6)
- Coagulation (PT, PTT, INR)
- Serum pregnancy test (for women of childbearing potential only)
- Hepatitis B and C and HIV serologies
- Cystoscopy and random biopsies
- Tumor assessment (CT scan)
- Fresh tumor biopsies collection are optional. This is only for those patients who signed the substudy informed consent.
- Urine samples collection (optional; only for patients included in ICO L'Hospitalet). The first urine in the morning would be collected using a standard testing tube of 50 ml.

### **8.1.2. Treatment phase**

Procedures to be conducted during the treatment phase of the study are presented in the Schedule of Assessments. Screening procedures performed within 72 hours of Cycle 1 Day 1 (C1D1) do not need to be repeated on C1D1.

The following procedures will be performed during the treatment phase:

- Complete physical exam
- ECOG Performance Status
- Vitals signs, weight and height
- ECG
- Review of concomitant medications
- Clinical laboratory tests for:
  - Clinical chemistry (see Table 4);
  - Hematology (see Table 5);
  - Urinalysis (see Table 6).
  - Thyroid function tests (TSH and T3 and T4)
- Adverse event/serious adverse event assessment
- Peripheral blood collection

### **8.1.3. End of treatment and follow-up visits**

The following procedures will be performed during the end of treatment visit (w12):

- Complete physical exam
- ECOG Performance Status
- Vitals signs, weight and height
- AE/SAE collection
- Concomitant medications
- Clinical laboratory tests for:
  - Clinical chemistry (see Table 4)
  - Hematology (see Table 5)
  - Urinalysis (see Table 6)
  - Coagulation (PT, PTT, INR)
  - Thyroid function tests (TSH and T3 and T4)
- Serum pregnancy test (for women of childbearing potential only)
- Tumor assessment by CT scan
- Peripheral blood collection
- Urine samples collection (optional; only for a group of patients).

### **8.1.4. Safety**

Safety follow-up visits will be scheduled up to 90 days after the last dose of study treatment, the procedures to be performed are the same that for EOT visit except for peripheral blood collection and CT scan that should not been performed in this visit, unless PI criteria as per normal practice

### **8.1.5. Follow-up Visits**

All patients will be followed for survival until the end of the study regardless of further treatments, or until the sponsor ends the study. It is of special interest the long-term follow-up of survival, disease free survival and the preservation of the bladder free of tumor.

Given the potential risk for delayed immune-related toxicities, safety follow-up must be performed up to 90 days after the last dose of durvalumab and tremelimumab administration.

The extended safety follow-up beyond 30 days after last study drug administration may be performed either via a site visit or via a telephone call with subsequent site visit requested in case any concerns noted during the telephone call.

## **8.2. Description of study procedures**

### **8.2.1. Medical history and physical examination, electrocardiogram, weight and vital signs**

Findings from medical history (obtained at screening) and physical examination shall be given a baseline grade according to the procedure for AEs. Increases in severity of pre-existing conditions during the study will be considered AEs, with resolution occurring when the grade returns to the pre-study grade or below.

Physical examinations will be performed on study days noted in the Schedule of Assessments.

### **8.2.2. Physical examination**

Physical examinations will be performed according to the assessment schedule. Full physical examinations will include assessments of the head, eyes, ears, nose, and throat and the respiratory, cardiovascular, GI, urogenital, musculoskeletal, neurological, dermatological, hematologic/lymphatic, and endocrine systems. Height will be measured at screening only. Targeted physical examinations are to be utilized by the Investigator on the basis of clinical observations and symptomatology. Situations in which physical examination results should be reported as AEs are described in Section 10.

### **8.2.3. Electrocardiograms**

Resting 12-lead ECGs will be recorded at screening, baseline, (cycle 1 Day 1 within 1 hr prior to the start of the first study treatment), and as clinically indicated throughout the study. ECGs should be obtained after the patient has been in a supine position for 5 minutes and recorded while the patient remains in that position. In case of clinically significant ECG abnormalities, including a QTcF value >470 ms, 2 additional 12-lead ECGs should be obtained over a brief period (e.g., 30 minutes) to confirm the finding.

Situations in which ECG results should be reported as AEs are described in Section 10.3.1

### **8.2.4. Vital signs**

Vital signs (blood pressure [BP], pulse, temperature, and respiration rate) will be evaluated according to the assessment schedules. Body weight is also recorded at each visit along with vital signs.

#### *8.2.4.1. First infusion*

On the first infusion day, patients in the durvalumab + tremelimumab combination therapy group will be monitored and vital signs collected/recorded in eCRF prior to, during and after infusion of IP as presented in the bulleted list below.

BP and pulse will be collected before, during, and after each infusion at the following times (based on a 60-minute infusion):

- Prior to the beginning of the infusion (measured once from approximately 30 minutes before up to 0 minutes [i.e., the beginning of the infusion])
- Approximately 30 minutes during the infusion (**halfway** through infusion)
- At the end of the infusion (approximately 60 minutes ±5 minutes)

If the infusion takes longer than 60 minutes, then BP and pulse measurements should follow the principles as described above or be taken more frequently if clinically indicated. A 1-hour observation period is recommended after the first infusion of durvalumab and tremelimumab.

#### *8.2.4.2. Subsequent infusions*

BP, pulse and other vital signs should be measured, collected/recorded in eCRF prior to the start of the infusion. Patients should be carefully monitored and BP and other vital signs should be measured during and post infusion as per institution standard and as clinically indicated. Any clinically significant changes in vital signs should be entered onto an unscheduled vital signs CRF page.

#### **8.2.5. Clinical laboratory tests**

Blood and urine samples for determination of clinical chemistry, hematology, and urinalysis will be taken at the times indicated in the assessment schedules and as clinically indicated (see Table 4 through Table 6).

Clinical laboratory safety tests, including serum pregnancy tests, will be performed in a licensed clinical laboratory according to local standard procedures. Sample tubes and sample sizes may vary depending on the laboratory method used and routine practice at the site. Urine pregnancy tests may be performed at the site using a licensed test (urine or serum pregnancy test). Abnormal clinically significant laboratory results should be repeated as soon as possible (preferably within 24 to 48 hours).

Additional safety samples may be collected if clinically indicated at the discretion of the Investigator. The date, time of collection, and results (values, units, and reference ranges) will be recorded on the appropriate eCRF.

The laboratory variables to be measured are presented in Table 4 (clinical chemistry), Table 5 (hematology), and Table 6 (urinalysis).

Other safety tests to be performed at screening include assessment for hepatitis B surface antigen, hepatitis C antibodies and HIV antibodies.

The following laboratory variables will be measured:

**Table 4. Clinical chemistry**

Albumin	Lipase b
Alkaline phosphatase	Magnesium c
ALT a	Potassium
Amylase b	Sodium
AST a	Total bilirubin
Bicarbonate c	Total protein
Calcium	TSH
Chloride c	T3 free d (reflex)
Creatinine clearance c	T4 free d (reflex)
Creatinine	Urea or blood urea nitrogen, depending on local practice
Gamma glutamyltransferase c	
Glucose	
Lactate dehydrogenase	

a Tests for ALT, AST, alkaline phosphatase, and total bilirubin must be conducted and assessed concurrently. If total bilirubin is  $\geq 2 \times$  ULN (and no evidence of Gilbert's syndrome), then fractionate into direct and indirect bilirubin.

b It is preferable that both amylase and lipase parameters are assessed. For sites where only 1 of these parameters is routinely measured then either lipase or amylase is acceptable.

c Bicarbonate (where available), chloride, creatinine clearance, gamma glutamyltransferase, and magnesium testing are to be performed at screening, on Day 0 (unless screening laboratory assessments are performed within 3 days prior to Day 0), and if clinically indicated.

d Free T3 or free T4 will only be measured if TSH is abnormal or if there is a clinical suspicion of an AE related to the endocrine system

**Table 5. Hematology**

Absolute neutrophil count	Absolute lymphocyte count
Hemoglobin	Platelet count

Note: For coagulation parameters, activated partial thromboplastin time and international normalized ratio are to be assessed at baseline and as clinically indicated.

Urinalysis should be done at baseline (screening) and then as clinically indicated

**Table 6. Urinalysis**

Bilirubin	Ketones
Blood	pH
Color and appearance	Protein
Glucose	Specific gravity

Note: Microscopy should be used as appropriate to investigate white blood cells and use the high power field for red blood cells.

If a patient shows an AST or ALT  $\geq 3 \times$  ULN together with total bilirubin  $\geq 2 \times$  ULN, refer to Appendix 1 for further instructions on cases of increases in liver biochemistry and

evaluation of Hy's Law. These cases should be reported as SAEs if, after evaluation, they meet the criteria for a Hy's law case or if any of the individual liver test parameters fulfill any of the SAE criteria.

All patients should have further chemistry profiles performed at 30 days ( $\pm 3$  days), 2 months ( $\pm 1$  week) and 3 months ( $\pm 1$  week) after permanent discontinuation of IP (see Table 4).

Any clinically significant abnormal laboratory values should be repeated as clinically indicated and recorded on the eCRF. Situations in which laboratory safety results should be reported as AEs are described in Section 10.3.5.

All patients with Grade 3 or 4 laboratory values at the time of completion or discontinuation from IP must have further tests performed until the laboratory values have returned to Grade 1 or 2, unless these values are not likely to improve because of the underlying disease.

### **8.3. Biological sampling procedures**

#### **8.3.1. Biomarker/pharmacodynamic sampling and evaluation methods**

##### *8.3.1.1. Peripheral blood*

Information about peripheral blood studies will be included in the informed consent form (ICF). Blood samples for biomarker analysis will be acquired at baseline (Week 1 prior to the administration of durvalumab and tremelimumab, W2 before initiation of RT, W8 at the end of RT, and W12 at the time of tumor response).

##### **Extraction and Manipulation Procedure:**

Every peripheral blood sample extraction for translational studies will consist in 2 whole blood tubes for peripheral blood mononuclear cells (PBMCs) isolation, 2 plasma tubes and 1 serum tube. A manual with the detailed procedures of extraction and manipulation of samples will be sent to each site. Plasma and serum tubes will be kept at  $-80^{\circ}\text{C}$  and shipped to the Translational Research Laboratory 1 at the Institut Català d'Oncologia (ICO) periodically. Whole blood for cytometry will be processed using Ficoll Hypaque  $\circledcirc$  and PBMCs will be frozen using FBS and DMSO, if this procedure is not available at the site, samples will be sent to the central laboratory in less than 24 hours.

The following translational studies are going to be performed:

- Correlation between changes in peripheral blood cell populations and clinical benefit. Combination of anti-CTLA4 and anti-PD1 leads to striking change in characteristics of circulating leukocytes *in vivo* (Rituparna et al. 2015). PBMCs will be analyzed using flow cytometry to determine the presence of activation and exhaustion

markers such as but not limited to PD1, CD137, and TIM3.

- Correlation between patient HLA type and clinical benefit and toxicity. Whole exome sequence (WES) from peripheral blood lymphocytes is going to be performed to use a comparator to WES from tumor metastasis. We are going to use this information to check the HLA types from different patient with outcome and toxicity.
- Correlation between blood circulating cytokines and clinical benefit. Changes in circulating cytokines have been associated to tumor response (Sammamed et al. 2014). Blood samples will be evaluated to determine variation in cytokines such as but not limited to IL-1a, IL-2, IL-6, IL-8, IFNy, and TGFb.
- Identification of exosome profile in peripheral blood. Exosomes are cell-derived vesicles that are present in many and perhaps all biological fluids, including blood, urine, and cultured medium of cell cultures. The reported diameter of exosomes is between 30 and 100 nm. It is becoming increasingly clear that exosomes have specialized functions and play key role in intercellular functions, and metastatic niche preparation. On the other hand, immune cells can secrete exosomes that can act as activators of immune response. The delivery and expose of molecules such as certain heat shock proteins (HSP) that can act as damage-associated molecular pattern molecules (DAMPS) and interact to several toll-like receptors (TLRs) can activate immune response. Additionally, dendritic cell-derived exosomes express MHC I, MHC II, and costimulatory molecules and have been proven to be able to induce and enhance antigen-specific T cell responses in vivo. (Benito-Martin et al. 2015). We are going to explore tumor exosomes (basal samples), and treatment-induced immune exosomes (induced by treatment) and correlate with treatment efficacy and toxicity.

#### *8.3.1.2. Urine samples*

Urine samples samples will be optionally required from patients recruited in ICO L'Hospitalet at the time of screening period and end of treatment visit. The first urine in the morning would be collected using a standard testing tube of 50 ml.

The urine will follow the standard procedures and should be delivered to the central laboratory at the Institut Català d'Oncologia (ICO) L'Hospitalet. If for any reason the urine can not be delivered to the central laboratory immediately it can be kept at room temperature.

The samples will be collected at the time of screening period and the end of treatment visit to detect and to quantify CD8 and CD4 lymphocytes and assess their immune profile (PD-1, TIM-3, CTLA-4, ICOS, and 4-1BB expression and TCR sequence.), in order to evaluate possible correlations between a high number of CD8-PDL1 with worse prognosis (as previously reported by [name], J. Exp. Med. 2018). Further analysis on could be implemented and will be detailed in the final Clinical Study Report.

#### **8.3.2. Estimate of volume of blood to be collected**

The total volume of blood that will be drawn from each patient in this study is as follows:

**Table 7. Volume of blood to be drawn from each patient**

Assessment		Sample volume (mL)	No. of samples	Total volume (mL)
Safety	Clinical chemistry	Local practice	Local practice	Local practice
	Hematology	Local practice	Local practice	Local practice
Biomarker analysis		45 mL	4	180

### 8.3.3 Fresh tumor biopsies

If the patient agrees to participate in the substudy a fresh tumor biopsy sample will be required at the time of initial TUR. A fragment of tumor tissue will be processed following standard procedures for formalin-fixing at the pathology unit, a suitable tumor block or 15 unstained slides 4 micrometer thick will be sent to the central laboratory. Another fragment of tumor tissue of at least 1 g of weight will be frozen immediately using an optimal cutting temperature (OCT) compound, tubes will be kept at -80°C and shipped to the central laboratory at the Institut Català d'Oncologia (ICO) periodically. Details for the processing, labelling and shipping of the samples will be given to each site in a manual.

*Tumor assessment:*

For every patients who have not achieved complete response will undergo a TUR and fresh biopsy will be obtained. One sample will be fixed in formalin and two additional ones will be frozen and kept at -80°C.

It will be required to send fresh and formalin fixed samples of the pathological surgical specimen from patients who are candidate to salvage cystectomy. For sample processing and sending please follow the same procedures explained above for the TUR.

Deep-frozen tissue will be processed according to standard laboratory procedures to isolate DNA and RNA.

*The following translational studies are planned:*

- Paraffin embedded tissue will be used for immunohistochemistry to study tumor inflammatory stroma (such as, but not limited to CD3; CD4; CD8; CD45RO; FoxP3; CD20, CD11b; CD68; among others), and lymphocyte exhaustion markers (PD-1; PD-L1; CD137; Granzyme B; Perforin; among others). Ventana SP263 (please see algorithm in appendix II) tumor infiltration and PD-L1 expression in tumor and stroma cells has been related to tumor response among different tumors and also in bladder cancer treated with PDL1 (Herbst et al. 2014).

- Correlation of neoantigen presentation and clinical benefit. Tumor mutational load is relevant to response to immunotherapy and has shown predictive value in bladder cancer treated with anti PDL1 (Rosenberg et al. 2016). We will perform whole exome-seq (WES), and RNA-seq to get information on tumor somatic mutations, included the amino-acid change in missense mutations, and its position into the protein. Additionally, we will predict the immune-peptides repertoire for each patient, combining information about missense mutations and inferred HLA alleles. DNA from tumor will be used to analyze TCR- $\beta$  chain clonality analysis to achieve information about T-cell diversity and clonality and associate to treatment benefit.
- Correlation of gene signatures and clinical response. Sequencing data will be used to classify the tumors according to the bladder cancer TCGA (<https://portal.gdc.cancer.gov/>). Previous data show correlation between subgroups and response (Rosenberg et al. 2016). DNA and RNA data will be used to explore gene signatures related to Interferon signaling and T cell activation.
- Explore changes in immune infiltrate, T-cell clonality and gene expression between pre- and post-treatment samples in non-responding patients using the techniques previously explained. This will allow us to determine the changes in immune cells and tumor and make hypothesis about resistance mechanisms.

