### **The following fields of data should be collected from PD-L1 testing laboratory:**

- Are the negative and positive controls stained correctly
- Is the H&E material acceptable
- Is morphology acceptable
- Total percent positivity of PD-L1 in tumor cells
- PD-L1 status (positive, negative or NA) in tumor cells

- Total percent positivity of PD-L1 in infiltrating immune cells

The Ventana SP263 assay to measure PD-L1 in tumors is experimental. As with all tests, there is a chance of false positive (the test shows high PD-L1 when it is not there) or false negative (the test does not show PD-L1 when it is there) results may occur.

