#### 11.2.2. Efficacy analyses and exploratory analyses

Table 8. *Efficacy analyses and exploratory analyses*

Objectives	Variable	Analysis	Clinical factors	Analysis population
Primary: efficacy of durvalumab plus tremelimumab with concurrent radiotherapy in terms of pathological response rate	Pathological response rate	1. Proportion estimation with a 95% confidence interval 2. Simon two stage decision rule 3. Logistic regression with clinical factors	Tumour size Tumour localization Histology Biomarkers	Per protocol
Secondary 1a: bladder preservation.	Rate of bladder preserved	1. Proportion estimation with a 95% confidence interval 2. Logistic regression with clinical factors	Tumour size Tumour localization Histology Biomarkers	Per protocol
Secondary 1b: bladder preservation.	Rate of immediate and late salvage cystectomies.	1. Proportion estimation with a 95% confidence interval 2. Logistic regression with clinical factors	Tumour size Tumour localization Histology Biomarkers	Per protocol

Secondary 1c: bladder preservation.	Time from start of immunotherapy to the date of recurrence of muscle invasive bladder carcinoma or metastases.	Kaplan Meier estimation of survival with a 95 % confidence interval	Not applicable	Per protocol
Secondary 1d: Overall survival	Time from treatment start to exitus.	Kaplan Meier estimation of survival with a 95 % confidence interval		Per protocol
Secondary 1.3: Progression free survival	Time from treatment start to tumour relapse or distant progression.	Kaplan Meier estimation of survival with a 95 % confidence interval		Per protocol
Secondary 2: Safety profile and tolerability of combination	CTCAE V4.03	1. Frequency table with adverse events, grades and relationship to study drugs and to radiotherapy treatment 2. Frequency table with severe toxicity.	Durvalumab cumulative dose, tremelimumab cumulative dose, radiotherapy treatment constraints (dose in risk organs).	Safety population
Secondary 3: To evaluate the long term functionalism and late sequel of the treatment in the preserved bladders.	Bladder control scale	Repeated measures analysis		Per protocol
Exploratory 1: Biomarkers and pathological response rate	Biomarkers and pathological response rate	Logistic regression in which response or not is the response and baseline biomarkers are factors to be studied	Biomarkers	Per protocol

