## APPENDIX 2. DURVALUMAB DOSE CALCULATIONS

For durvalumab dosing done depending on patient weight:

1. Cohort dose: X mg/kg
2. Patient weight: Y kg
3. Dose for patient:  $XY \text{ mg} = X \text{ (mg/kg)} \times Y \text{ (kg)}$
4. Dose to be added into infusion bag:

Dose (mL) =  $XY \text{ mg} / 50 \text{ (mg/mL)}$  where 50 mg/mL is durvalumab nominal concentration.

The corresponding volume of durvalumab should be rounded to the nearest tenth mL (0.1 mL). Dose adjustments for each cycle are only needed for greater than 10% change in weight.

5. The theoretical number of vials required for dose preparation is the next greatest whole number of vials from the following formula:

Number of vials = Dose (mL) / 10.0 (mL/vial)

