### 3.2.8.PD-L1

Table 26: PD-L1 High status

	(N=)
PD-L1 High status	
Missing data	
Low/Negative	
High	

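### The SAP analyses PD-L1 only as an undefined High versus Low/Negative split and leaves out the model of pathological response on biomarkers that the protocol specifies

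*Combined protocol and SAP*

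**What the plan says.** **Protocol, scoring rule.** Section 8.3.3 refers to "Ventana SP263 (please see algorithm in appendix II". The appendix with that number is "APPENDIX 2. DURVALUMAB DOSE CALCULATIONS", and none of the five appendices in the table of contents is a PD-L1 algorithm. The PD-L1 Testing subsection requires the assay to be run according to its package insert. It says that data supporting a cut-off and scoring algorithm exist for two other tumour types, and places bladder among those where evidence on clinical performance is limited.

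**Protocol, data to be collected.** The testing laboratory is to return three scores: "Total percent positivity of PD-L1 in tumor cells", "PD-L1 status (positive, negative or NA) in tumor cells" and "Total percent positivity of PD-L1 in infiltrating immune cells".

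**Protocol, analysis.** Table 8 in section 11.2.2 (Exploratory 1) specifies: "Logistic regression in which response or not is the response and baseline biomarkers are factors to be studied". It does not say in what form each biomarker enters.

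**SAP.** Section 3.2.8 introduces the variable in "Table 26: PD-L1 High status", with rows for missing, Low/Negative and High. The same two groups are used in Tables 118–120 (EFS bladder preservation), 143–145 (EFS specific), 167–169 (PFS) and 191–193 (OS), and in the Cox models of Tables 124, 127, 149, 173 and 197. No table reports or models either percentage. The primary efficacy section (3.8) contains no PD-L1 model.

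**The concern.** A two-group variable is only as well specified as the rule that forms the groups. Here the rule is not in the documents, and the laboratory's positive/negative/NA status for tumour cells is not mapped to High and Low/Negative. If the threshold or the compartment can still be settled when outcomes are known, a nominal p-value no longer means what it says. Even an honestly fixed split discards gradation in scores that the protocol wants recorded, in a trial of at most 32 patients.

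The question the protocol poses, biomarkers against pathological response, has no table in the SAP. PD-L1 is the only biomarker among the SAP's seven prognostic factors, so this is where the exploratory biomarker objective would be reported.

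**Working it through.** The documents give no sample size, power or error rate for PD-L1, so there is no planned figure to reproduce. The check has three parts.

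**1. Can High be traced to a rule?**

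| Place | What it supplies |
|---|---|
| Protocol 8.3.3, algorithm reference | Leads to durvalumab dosing |
| Protocol 8.3.3, PD-L1 Testing | Package insert, not reproduced; no bladder cut-off named |
| Protocol 8.3.3, sample quality | More than 100 tumour cells: sample adequacy, not positivity |
| Laboratory fields | Two percentages and a tumour-cell status; no High category |
| SAP 3.2.8, Table 26 | Category labels without definition |

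The scores are specified; the rule that turns them into High is not stated.

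**2. Was the SAP written before data were seen?** Its title page is marked as a 2022 manuscript. Section 3.1 says that all 32 patients meet the population conditions. Table 36 lists particular radiotherapy values, such as 66 sessions and 61 Gy. Tables 52 to 55 have a Yes row for late cystectomy at 9 months but not at 3 or 6, which suggests, without proving, that outcomes had been seen too.

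**3. Size, illustrative only.**

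*Information kept by a split.* For a normal marker with a linear effect and a share q rated High, the split keeps φ(z)² / [q(1 − q)], where z is the normal quantile at 1 − q.

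- q = 0.5: 0.3989² / 0.25 = 0.159 / 0.25 = 0.637
- q = 0.3: 0.3477² / 0.21 = 0.121 / 0.21 = 0.576
- q = 0.2: 0.2800² / 0.16 = 0.0784 / 0.16 = 0.490

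If all 32 patients had PD-L1, that would be worth about 20.4, 18.4 and 15.7 patients. Table 26 has a missing-data row and the Cox tables carry a second model without PD-L1, so the true denominator may be smaller.

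Skew changes these shares. For a tumour-cell percentage distributed as 100 × Beta(0.4, 1.2), an assumption, the squared correlation of the split with the raw score is q(1 − q)(m₁ − m₀)² / variance, where m₁ and m₀ are the mean scores above and below the cut:

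- cut at 1%: 0.826 × 0.174 × (30.2 − 0.3)² / 721 = 0.18
- cut at 25%: 0.380 × 0.620 × (54.4 − 7.0)² / 721 = 0.73

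*False positives when the rule is open.* The simulation had 10,000 null trials of 32 patients and a two-sided 0.05 level. It took the smallest log-rank p over the permitted definitions, with at least 3 patients per group. Assumptions not from the documents: independent tumour-cell and immune-cell scores, 100 × Beta(0.4, 1.2) and 100 × Beta(0.5, 1.2); exponential event times with median 36 months; uniform censoring from 18 to 40 months.

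| Freedom in the rule | Log-rank p < 0.05 |
|---|---|
| Tumour cells at 25%, fixed | 0.053 |
| Tumour cells, three cut-offs (1, 10, 25%) | 0.128 |
| Tumour cells, five cut-offs (1, 5, 10, 25, 50%) | 0.183 |
| Tumour cells, immune cells or either, at 25% | 0.126 |
| Tumour cells, immune cells or either, five cut-offs | 0.375 |

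A repeat with a different random seed gave 0.051, 0.129 and 0.382 for the first, fourth and fifth rows. The log-rank test is a close stand-in for the SAP's univariate Cox Wald test. The 25% threshold is an example, not a proposal.

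**The case against.** The strongest defence is that PD-L1 is exploratory, is one of seven prognostic factors, and drives no decision rule. The assay must follow its package insert, which may contain a scoring rule, and protocol Table 8 already plans the response model; a set of SAP table shells does not withdraw it. Most of this stands, and it limits the point to an inexpensive improvement.

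Several stronger readings are tempting, and the documents do not support them:

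- *That no cut-off exists.* They show only that none is stated. The insert cannot be consulted here, though the protocol itself does not present it as settled for bladder.
- *That the cut-off was picked after outcomes were known.* Nothing shows a search. The documents merely offer no protection against one.
- *That High cannot be derived from the collected data.* A stated rule on one or both percentages could produce it.
- *That the error rate is that of an exhaustive search.* Trying every split that puts 6 to 26 patients in a group gives about 18% with Fisher's test on response, but the SAP plans neither that search nor that test.

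The remedy has a weakness of its own. Choosing a scale for skewed percentages now is also a late choice, and if the true effect is a threshold, a linear term can be the poorer model.

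**Conclusion.** The point holds as a gap in an exploratory analysis. The split labelled "PD-L1 High status" has no stated cut-off or compartment, the only pointer to an algorithm leads to the wrong appendix, and the SAP gives no analysis of PD-L1 against pathological response despite the protocol's specification.

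The sizes are indicative. The share of information kept, 64% to 49%, rests on a normal marker, a linear effect and complete data; under the skewed example it ran from 18% to 73% depending on the cut. The rise from about 5% to about 13% rests on the assumed score and event-time distributions and on one open choice of compartment; several cut-offs would raise it further. The finding does not touch the primary endpoint, the two-stage rule or the sample size.

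**What to change.** In the SAP:

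1. Add a one-predictor logistic model of pathological response (the protocol's Exploratory 1) and a one-predictor Cox model of bladder-preservation EFS. Fit each to the tumour-cell percentage and to the immune-cell percentage separately, on one scale fixed in advance, for example rank or log.
2. Report how many patients have PD-L1 data for each model.
3. Keep the High versus Low/Negative tables as secondary. Take the cut-off and compartment from a cited, dated scoring rule and map the laboratory categories to it; otherwise label the split post hoc.
4. Label all PD-L1 results exploratory.

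In the protocol, correct the appendix reference in section 8.3.3.

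The cost is wording and four small fits (two scores by two outcomes) on data the protocol already asks the laboratory to return; whether the percentages were recorded for every patient must be confirmed. The downsides are a few more exploratory tests, a scale choice for skewed scores, and results less easily shown as two Kaplan–Meier curves.
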